8.4. Variables

Exposure

- **Phase I of the study:** PAC (UFH [Anatomical Therapeutic Chemical [ATC] code: B01AB01], LMWH [B01AB04, B01AB05, B01AB06, B01AB12], VKA (warfarin [B01AA03]), NOACs (apixaban [B01AF02], rivaroxaban [B01AF01], edoxaban [B01AF03], dabigatran [B01AE07])
- **Phase II of the study:** Apixaban (B01AF02), Rivaroxaban (B01AF01), Edoxaban (B01AF03), Dabigatran (B01AE07), Warfarin (B01AA03)

Outcome(s)

- **Phase I of the study**

- Sociodemographic and clinical characteristics of patients with VTE who initiated anticoagulants.
- Utilization of different anticoagulants at treatment initiation. Patients will be classified based on their index anticoagulant treatment received within 30 days after being diagnosed with VTE.
- Treatment interruption from the index anticoagulant treatment, which will be defined as when a patient has a gap with no new treatment within 30 days of the estimated end of supply, but subsequently restarts the index treatment after this period.[1] The time to treatment interruption will be defined as the period from the index date to the date of treatment interruption.
- Treatment switching will be defined as a prescription of another anticoagulant therapy that is started after the treatment initiation of the index anticoagulant treatment and within 30 days after the estimated end of supply of the index anticoagulant drug (exposure to the new anticoagulant treatment must last for at least 30 days to be considered as a treatment switch). The time to treatment switch will be defined as the period from the index date to the date of treatment switch.

Exemption: As heparin can be initiated at acute stage of DVT/PE before clinical decision to use OAC, a switch from initial heparin treatment to an OAC within 2 weeks after heparin treatment initiation will not be considered a treatment switch.

- Treatment discontinuation (complete discontinuation; no reinitiation) will be defined as when a patient who ended their first continuous treatment episode with the index anticoagulant treatment without switching, and subsequently have no further prescriptions for that respective anticoagulant treatment during all available follow-up time. The time to treatment discontinuation will be defined as the period from the index date to the date of treatment discontinuation.
- Overall anticoagulant treatment duration will be defined as the time period from the index date to the earliest of treatment interruption, switch, or discontinuation.
- If a patient has evidence of a repeat prescription within 30 days of the end of their prescription and does not experience any of the above events (treatment interruption, switch, or discontinuation), they will be assumed to be persistent on treatment.[1]
- Clinical event preceding first treatment change will be defined as occurrence of any event listed below within 30 days before treatment interruption, switch, or discontinuation. A new clinical event will be considered 'new' when it occurs for the first time within a 6-month period for acute conditions (arterial thromboembolism, ischemic stroke, transient ischemic attack, myocardial infarction, angina pectoris, acute kidney injury, and abnormal liver function) and 5-years for chronic conditions (cancer, chronic kidney disease, and liver disease). A patient may contribute to multiple events.
 - ① Major bleeding (as defined in Phase II)
 - ② Complications of VTE: post-thrombotic syndrome and chronic thromboembolic pulmonary hypertension
 - ③ Thromboembolism: PE diagnosis in patients with index event as DVT only, new diagnosis of arterial thromboembolism, ischemic stroke, transient ischemic attack, myocardial infarction, or angina pectoris
 - ④ Major surgery: orthopedic surgeries (knee arthroplasty, hip arthroplasty, and hip fracture surgery), cancer surgeries (stomach, colorectal, hepatobiliary, pancreatic, breast, ovarian, cervical, renal, bladder, prostate, lung, and esophageal cancers, and brain tumors), and benign surgeries (myomectomy, oophorectomy, and transurethral resection of the prostate)
 - ⑤ Cancer-related event (among non-active cancer patients only): new diagnosis of active cancer
 - ⑥ Kidney function change: new diagnosis of chronic kidney disease or acute kidney injury
 - ⑦ Liver function change: new diagnosis of liver disease or abnormal liver function

Clinical event preceding first treatment change	ICD-10 diagnosis code
Major bleeding	Defined in Phase II
Complications of VTE	
Post-thrombotic syndrome	I87.0
Chronic thromboembolic pulmonary hypertension	I27.2
Thromboembolism	
PE diagnosis	I26.0, I26.9
Atrial thromboembolism	I74
Ischemic stroke	I63
Transient ischemic attack	G45.9
Myocardial infarction	I21
Angina pectoris	I20
Major surgery	
Orthopedic surgeries	N0305, N0601, N0611, N0641, N0711, N2070, N0715, N2710, N0731, N0981, N0991, N1711, N3710, N1721, N3720, N1715, N4710, N1725, N4720, N2072, N2077, N2712, N2717, N3712, N3717, N3722, N3727, N4712, N4717, N4722, N4727
Cancer surgeries	Specified in 'cancer-related surgery' of section 8.3.2
Benign surgeries	R4123-R4129, R4421, R4430, R3975
Cancer-related event (active cancer)	C00-C97 (excluding non-melanoma skin cancer, C44) with V code (V011, V027, V193, V194)
Kidney function change	
Chronic kidney disease	N18, N19
Acute kidney injury	N17
Liver function change	
Liver disease	B15-B19, K70-K77
Abnormal liver function	R94.5, R74.0

- **Phase II of the study**

- Major bleeding will be defined using primary or secondary diagnosis codes according to the ICD-10 diagnostic codes shown in below table and classified by site (intracranial, gastrointestinal [GI], all others).

Major bleeding	ICD-10 diagnosis code	Diagnostic definition
Intracranial hemorrhage	I60, I61, I62, I690, I691, I692, S064, S065, S066, S068	Diagnosis code + admission code + brain CT or MRI code

		* Brain CT or MRI: CT: HA441, HA451, HA461, HA471, HA851 MRI: HE101, HE102, HE135, HE201, HE202, HE235, HE301, HE302, HE401, HE402, HE501, HE502, HE535
GI bleeding	I850, I983, K2211, K226, K228, K250, K252, K254, K256, K260, K262, K264, K266, K270, K272, K274, K276, K280, K282, K284, K286, K290, K3181, K5521, K625, K920, K921, K922	Diagnosis code + admission code
Other bleeding	D62, H448, H3572, H356, H313, H210, H113, H052, H470, H431, I312, N020-N029, N421, N831, N857, N920, N923, N930, N938, N939, M250, R233, R040, R041, R042, R048, R049, T792, T810, N950, R310, R311, R318, R58, T455, Y442, D683	Diagnosis code + admission code

- The earliest date of diagnosis of the major bleeding event after the index date will be defined as the outcome occurrence date.
- Patients will be followed up from the index date to the occurrence of an outcome, treatment discontinuation (30-day grace period), switch to another anticoagulants, in-hospital death, or end of the study period (31 Dec 2019) whichever comes first.

Potential Confounder(s)

- Sociodemographic characteristics such as age, sex, and index year will be assessed at the index date.
- CCI [2] and HAS-BLED [3] scores will be measured within the 6-month period prior to the index date.

List of CCI	Score	ICD-10 codes
Cerebrovascular disease	1	G45, G46, H34, I60-I69
Congestive heart failure	1	I09.9, I11.0, I13.0, I13.2, I25.5, I42.0, I42.5-I42.9, I43, I50, P29.0
Chronic pulmonary disease	1	I27.8, I27.9, J40-J47, J60-J67, J68.4, J70.1, J70.3

Dementia	1	F00–F03, F05.1, G30, G31.1
Diabetes without chronic complication	1	E10.0, E10.1, E10.6, E10.8, E10.9, E11.0, E11.1, E11.6, E11.8, E11.9, E12.0, E12.1, E12.6, E12.8, E12.9, E13.0, E13.1, E13.6, E13.8, E13.9, E14.0, E14.1, E14.6, E14.8, E14.9
Mild liver disease	1	B18, K70.0-K70.3, K70.9, K71.3-K71.5, K71.7, K73, K74, K76.0, K76.2-K76.4, K76.8, K76.9, Z94.4
Myocardial infarction	1	I21, I22, I25.2
Peripheral vascular disease	1	I70, I71, I73.1, I73.8, I73.9, I77.1, I79.0, I79.2, K55.1, K55.8, K55.9, Z95.8, Z95.9
Peptic ulcer disease	1	K25-K28
Rheumatologic disease	1	M05, M06, M32–M34, M31.5, M35.1, M35.3, M36.0
Diabetes with chronic complication	2	E10.2–E10.5, E10.7, E11.2–E11.5, E11.7, E12.2–E12.5, E12.7, E13.2–E13.5, E13.7, E14.2–E14.5, E14.7
Hemiplegia or paraplegia	2	G04.1, G11.4, G80.1, G80.2, G81, G82, G83.0-G83.4, G83.9
Any malignancy, including leukemia and lymphoma	2	C00–C26, C30–C34, C37–C41, C43, C45–C58, C60–C76, C81–C85, C88, C90–C97
Renal disease	2	I12.0, I13.1, N03.2-N03.7, N05.2–N05.7, N18, N19, N25.0, Z49.0–Z49.2, Z94.0, Z99.2
Moderate or severe liver disease	3	I85.0, I85.9, I86.4, I98.2, K70.4, K71.1, K72.1, K72.9, K76.5, K76.6, K76.7
AIDS/HIV	6	B20–B22, B24
Metastatic solid tumor	6	C77-C80

List of HAS-BLED	Score	ICD-10 codes

Hypertension	1	I10-I15
Abnormal renal function	1	N18.3, N18.4, N18.5, N19, Z94.0, Z99.2
Abnormal liver function	1	B15-B19, C22, D68.4, I98.2, I98.3, K70-K77, Z94.4
Stroke	1	I63, I69.3, G45.9
Bleeding history	1	Intracranial and GI: I60, I61, I62, I69.0, I69.1, I69.2, S06.4, S06.5, S06.6, S06.8, I85.0, I98.3, K22.11, K22.6, K22.8, K25.0, K25.2, K25.4, K25.6, K26.0, K26.2, K26.4, K26.6, K27.0, K27.2, K27.4, K27.6, K28.0, K28.2, K28.4, K28.6, K29.0, K31.81, K55.21, K62.5, K92.0, K92.1, K92.2 Other sites*: D62, H44.8, H35.72, H35.6, H31.3, H21.0, H11.3, H05.2, H47.0, H43.1, I31.2, N02.0-N02.9, N42.1, N83.1, N85.7, N92.0, N92.3, N93.0, N93.8, N93.9, M25.0, R23.3, R04.0, R04.1, R04.2, R04.8, R04.9, T79.2, T81.0, N95.0, R31.0, R31.1, R31.8, R58, T45.5, Y44.2, D68.3
Labile INR	1	Not applicable
Elderly > 65 years	1	
Drugs or alcohol concomitantly	1	Antiplatelet agents, NSAIDs
	1	Alcoholism: E24.4, F10, G31.2, G62.1, G72.1, I42.6, K29.2, K70, K86.0, O35.4, R78.0, T51.0, X45, X65, Y15, Y90, Y91, Z71.4, Z72.1

*Blood transfusion (Korean Procedure Codes: X1001, X1002, X2011, X2012, X2021, X2022, X2031, X2032, X2041, X2042, X2051, X2052, X2061, X2062, X2071, X2072, X2081, X2082, X2091, X2092, X2101, X2102, X2111, X2112, X2121, X2122, X2131, X2132, X2141, X2142, X3010) will also be used to define other site bleeding history.

- Initial presentation of VTE
 - DVT (I80.2, I80.3)

- PE (I26.0, I26.9)
- Both DVT and PE
- Comorbidities (ICD-10 diagnostic code) will be measured within the 6-month period prior to the index date.
 - Antiphospholipid syndrome (D68.6, I82.9): As diagnosis of antiphospholipid syndrome is usually made after VTE diagnosis with subsequent diagnostic procedures, its presence will be evaluated within the 6-month period after the index date.
 - Asthma (J45)
 - Cancer (C00-C97): History of cancer (non-active) will be evaluated within a lifetime prior to the index date.
 - Chronic obstructive pulmonary disease (COPD; J40-J44)
 - Chronic kidney disease (N18, N19)
 - Chronic liver disease (B18, B19, K70-K77)
 - Diabetes mellitus (E10-E14)
 - Fracture (S22, S32, S42, S52, S62, S72, S82, S92, T10, T12)
 - Heart failure (I50)
 - Hyperlipidemia (E78)
 - Hypertension (I10-I15)
 - Ischemic heart disease (I24, I25)
 - Myocardial infarction (I21)
 - Stroke (I60-I64, I69, G45)
 - Trauma (T79, T98, V01–V99, W11–W17, W50–W52, W64, X34–X39, Y01–Y04, Y30–Y32)
- Previous use of medications (WHO-ATC code) will be measured within the 6-month period prior to the index date.
 - Corticosteroids (H02)
 - Nonsteroidal anti-inflammatory drugs (NSAIDs; M01A)
 - Angiotensin-converting enzyme (ACE) inhibitors (C09A, C09B)

- Angiotensin II receptor blockers (ARBs; C09C, C09D)
- Antiplatelet agents (aspirin [N02BA01], aspirin/dipyridamole [B01AC30], abciximab [B01AC13], beraprost [B01AC19], cilostazol [B01AC23], clopidogrel [B01AC04], iloprost [B01AC11], indobufen [B01AC10], limaprost [C04AX], ozagrel [R03DX], prasugrel [B01AC22], sarpogrelate [B01AC], ticagrelor [B01AC24], ticlopidine [B01AC05], tirofiban [B01AC17], treprostinal [B01AC21], triflusal [B01AC18])
- Azole antifungal agents (fluconazole [J02AC01], itraconazole [J02AC02], voriconazole [J02AC03], posaconazole [J02AC04])
- β -blockers (C07)
- Calcium-channel blockers (C08)
- Selective serotonin reuptake inhibitors (SSRIs; N06AB)
- Proton pump inhibitors (PPIs; A02BC)
- Diuretics (C03)
- Thiazides (C03A)
- Vasodilators (C01D, C04A)
- Estrogens (G03C)
- Cyclooxygenase (COX)-2 inhibitors (M01AH)

- Number of outpatient visits within the 6-month period prior to the index date.

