- Had a record of active cancer, defined as first diagnosis of cancer with V code (a special code applied to patients with confirmed diagnosis of cancer by Korean Ministry of Health and Welfare for reimbursement for 5 years or longer if recurrent/metastatic) within the past 6 months of period prior to index date; or receiving anti-cancer treatment (chemotherapy, radiation therapy, or cancer-related surgery) under cancer diagnosis with V code within the past 6 months period prior to index date

Follow-up

- **Phase I of the study:** Patients will be followed-up from the index date until the earliest of in-hospital death or end of the study period (31 Dec 2019).
- **Phase II of the study:** Patients will be followed-up from the index date until the earliest of outcome occurrence (bleeding event), treatment discontinuation, switch to another anticoagulant, in-hospital death, or end of the study period (31 Dec 2019), where patients will be considered to have discontinued treatment when new prescription is absent within the 30-day grace period after the end of the former prescription.

- **Variables**

Exposure(s)

- Anticoagulant therapy (PAC [LMWH, UFH, others], NOACs [apixaban, dabigatran, rivaroxaban, edoxaban], warfarin).

Outcome(s)

- **Phase I of the study:** sociodemographic and clinical characteristics of patients with VTE, utilization of index anticoagulant treatment, treatment patterns (including treatment interruption, switching, complete discontinuation), overall treatment duration, and clinical events preceding first treatment change
- **Phase II of the study:** Primary or secondary diagnosis with major bleeding (by site: intracranial, gastrointestinal [GI], and other sites) after the index date

Covariate(s)

- Sociodemographics (age, sex) will be assessed on the index date. Clinical characteristics including comorbidities, previous use of medications, and the number of outpatient visits will be assessed within the 6-month period prior to the index date

- **Data sources**

- South Korea's Health Insurance and Review Assessment Service (HIRA) database

- **Study size**

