7. DATA SOURCES

We will use the nationwide HIRA database of South Korea between 1 Mar 2012 and 31 Dec 2019 to identify all variables (exposure, outcome, covariates) needed to conduct this study. The HIRA database includes healthcare utilization information of residents of South Korea, with patient identifiers anonymized. Information on age, sex, diagnosis (ICD-10 diagnostic code, date of diagnosis, setting of diagnosis [inpatient, outpatient, emergency department], and others), medications dispensed/prescribed (national drug chemical code based on the active ingredient, date of prescription, days' supply, dose, route of administration, and others). Previous validation study that compared diagnosis codes recorded in the HIRA to those of recorded in electronic medical records found an overall positive predictive value (PPV) of 82.3%.

[figure not shown]

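### Phase II censors at a switch it does not define; the only definition, under Phase I, needs 30 days on the new drug, so censoring could depend on an early bleed

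*SAP*

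**What the plan says.** SAP 8.4 and protocol 9.3 define a treatment switch once, under the Phase I outcomes. The new anticoagulant must start after the index drug "and within 30 days after the estimated end of supply of the index anticoagulant drug", and "exposure to the new anticoagulant treatment must last for at least 30 days to be considered as a treatment switch". On dating, the text says only: "The time to treatment switch will be defined as the period from the index date to the date of treatment switch". It does not say whether that date is the first new prescription or the day the 30-day test is met.

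For Phase II the SAP says: "Patients will be followed up from the index date to the occurrence of an outcome, treatment discontinuation (30-day grace period), switch to another anticoagulants", followed by in-hospital death and the end of the study period. Protocol 9.3, the protocol abstract and the notes to the study schematic agree. None of them defines a switch again or refers to the Phase I definition.

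The abstract treats a Phase II patient as discontinued when a "new prescription is absent within the 30-day grace period after the end of the former prescription". It does not say whether the censoring date is the end of supply or the end of grace.

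The outcome date does not depend on the drug being taken: "The earliest date of diagnosis of the major bleeding event after the index date will be defined as the outcome occurrence date".

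The sensitivity analyses in SAP section 10 and its Table 20 vary the grace period to 15 and 60 days. None varies the 30-day switch requirement.

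**The concern.** An on-treatment analysis needs a censoring rule that can be applied on the day the treatment changes. The 30-day requirement cannot be applied then, because it looks forward and its answer can be set by the outcome itself. Take two patients who leave warfarin for a NOAC on the same day. One stays on the NOAC for 30 days and counts as a switcher. The other bleeds on day 10 and stops it, so under this definition has not switched. If warfarin supply or grace is still running, the bleed is recorded as a warfarin event.

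The error removes censoring selectively in patients with early bleeds after a change, in the primary comparison of Phase II. Where switching is unequal between the arms, the hazard ratio moves.

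**Working it through.** **No stated figure to reproduce.** The point turns on a definition. The study-size figures do not depend on it. As a check, Schoenfeld's formula for apixaban at HR 0.75 gives 397.6 events, and 397.6 / 0.0119 = 33,408 patients against the stated 33,340.

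**Which bleeds are affected.** Suppose the Phase I definition is used, exposure to the new drug ends before 30 days, and the discontinuation rule refers to the index drug. Let day 0 be the end of index-drug supply, s the day of the change, and b = 1 to 29 the bleed day counted from the change. The bleed is charged to the index drug if s + b ≤ C, where C = 30 if discontinuation is dated at end of grace and C = 0 if at end of supply.

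| Day of change s | Bleed days charged, C = 30 | Bleed days charged, C = 0 |
|---|---|---|
| -30 | 29 of 29 | 29 of 29 |
| -15 | 29 of 29 | 15 of 29 |
| -7 | 29 of 29 | 7 of 29 |
| 0 | 29 of 29 | 0 of 29 |
| +10 | 20 of 29 | 0 of 29 |
| +20 | 10 of 29 | 0 of 29 |
| +30 | 0 of 29 | 0 of 29 |

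With the 60-day grace period dated at its end (C = 60), all 29 days are charged for any change up to day +30. So the unstated discontinuation date decides how many early bleeds are misattributed.

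**Size, on assumptions.** The documents give no switch rate and no bleeding risk after a switch. Assume that 5% to 20% of warfarin users switch, that 0.5% to 1% of switchers bleed within 30 days, that every such bleed stops the new drug early and falls inside index follow-up, and that no NOAC user switches.

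- Misattributed bleeds per warfarin user: 0.05 × 0.005 = 0.025%, up to 0.20 × 0.01 = 0.20%.
- Relative excess = that share / planned event probability. A true HR of 1.00 becomes 1 / (1 + excess). The planned overall probability stands in for the warfarin rate.

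| Comparison | Planned probability | Excess | Apparent HR |
|---|---|---|---|
| Apixaban | 1.19% | 2.1% to 16.8% | 0.98 to 0.86 |
| Dabigatran | 1.4% | 1.8% to 14.3% | 0.98 to 0.88 |
| Rivaroxaban | 8.1% | 0.3% to 2.5% | 0.997 to 0.976 |
| Edoxaban | 8.5% | 0.3% to 2.4% | 0.997 to 0.977 |

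**A second view, starting from extra events.** For apixaban, 49,224 × 0.0119 = about 586 events. At HR 0.75 with 39.3% on apixaban, the apixaban share is 0.393 × 0.75 / (0.393 × 0.75 + 0.607) = 0.327, or about 191 events, leaving about 394 on warfarin. Assume 0.5% to 5% extra events in one arm:

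- Added to warfarin (about 2 to 20 events): 0.75 / 1.005 = 0.746, down to 0.75 / 1.05 = 0.714.
- Added to apixaban (about 1 to 10 events): 0.75 × 1.005 = 0.754, up to 0.75 × 1.05 = 0.788.

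**The case against.** The strongest reply is that the 30-day rule is a Phase I definition and Phase II has its own follow-up rule. The Phase II discontinuation rule differs from the Phase I one, which requires no reinitiation at all, so Phase I definitions are not carried over wholesale. Where the SAP shares a definition between phases, as for major bleeding, it says so. Read literally, the Phase II text could already censor at any change of anticoagulant. This stands: use of the 30-day rule in Phase II is an inference. It does not remove the problem, because a programmer who needs a switch rule will find only this one. The Phase II sensitivity analysis also varies treatment interruption, a term defined only in Phase I. At best the text allows two censoring rules for the primary comparison.

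A reader might infer that every bleed within 30 days of a change is charged to the old drug. The documents do not support that. The test is length of exposure, not 30 days free of bleeding. If the new drug is continued after the bleed, the switch can qualify. It can also qualify if a first supply of 30 days or more counts as exposure; the database records "days' supply, dose, route of administration, and others", and the SAP does not say how exposure is measured. A qualifying switch dated at the new prescription censors the patient before the bleed.

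The size is also open to challenge. The assumed 0.5% to 1% risk in 30 days is 42% to 84% of the whole planned 1.19%, so the upper end is extreme. Varying the grace period tests part of the same window, but not the 30-day requirement.

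**Conclusion.** The point holds in conditional form. Phase II lacks a switch definition, and the only one available makes censoring depend on events after the change, including the outcome. Bleeds are misattributed when three things coincide: the Phase I definition is used, a bleed or death ends the new drug before 30 days, and index supply (or grace, if discontinuation is dated at its end) has not run out.

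A reader might also infer that every NOAC hazard ratio is biased downward. That follows only if warfarin users switch more than NOAC users. It is plausible, since enrolment starts in March 2013 and the reimbursement expansion for NOACs came in May 2015, but neither document gives switch rates. If NOAC users switch more, the bias runs the other way. The HR of 0.86 is the far end of an assumed range at the lowest planned event probability; at 8.1% to 8.5% the same excess moves a ratio of 1.00 by less than 0.03.

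This is more than a missing detail, because an available rule avoids the dependence on the outcome and uses prescription dates already in the data. It should be settled before Phase II is programmed.

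**What to change.** In SAP 8.4 and protocol 9.3, under Phase II, and to match in the protocol abstract:

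- State that follow-up is censored on the date of the first prescription of a different oral anticoagulant, whatever its duration.
- State how a move to a parenteral anticoagulant is handled. The present Phase II wording covers any anticoagulant, so a rule limited to oral drugs would narrow it without saying so. Say also whether the two-week heparin exemption, which belongs to the Phase I definition, applies.
- State whether discontinuation is dated at end of supply or end of grace.
- Keep the 30-day requirement for the Phase I description of switching only. If it is kept in Phase II, say how the 30 days are measured and add a sensitivity analysis that censors at the first prescription of any other anticoagulant.

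The cost is a few sentences in each document and no new data. The downside is that a short trial of another drug ends follow-up slightly earlier.

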5. INTRODUCTION

Venous Thromboembolism (VTE), which includes deep vein thrombosis (DVT) and pulmonary embolism (PE), is a major cause of morbidity, mortality and healthcare expenditure. Although the occurrence of VTE in the Asian population has been lower than in Western populations, Its incidence has been reported to have increased rapidly in recent years.

For pharmacologic treatment of patients with VTE without cancer, the American College of Chest Physicians (CHEST) guidelines recommend the use of Non-Vitamin K antagonist oral anticoagulants (NOACs) over Vitamin K Antagonists (VKAs), with supporting evidences suggesting that each NOAC (e.g., apixaban) is effective at preventing recurrent VTE. In more recent treatment guidelines for the management of VTE released by the American Society of Hematology (ASH), NOACs are still recommended over VKAs for the initial management of VTE. NOACs are classified as new generation of anticoagulants with approved indications of the risk reduction of stroke and embolism in nonvalvular atrial fibrillation (NVAF) as well as prophylaxis and treatment of DVT and PE.

All NOACs became available as the first-line treatment of acute VTE in Korea after reimbursement expansion in May 2015. However, despite the increasing use of NOACs among VTE patients, there are still limited real-world evidence that assess treatment patterns as well as effectiveness and safety of the different anticoagulants especially among Asian population.

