10. STATISTICAL ANALYSIS

All statistical analyses will be performed using SAS Enterprise Guide 7.1 (SAS Institute Inc., Cary, NC, USA), provided by HIRA through a virtual access machine.

Phase I of the study (descriptive)

Main Analysis

- Descriptive analysis will be conducted separately in two cohorts of non-cancer VTE and cancer VTE patients according to co-presence of active cancer.
- Sociodemographic and clinical characteristics will be summarized with means (standard deviations [STD]) or median (interquartile range [IQR]) for continuous variables and with count (proportions) for categorical variables for the three treatment groups of interest: PAC only (UFH, LMWH, UFH+LMWH), warfarin-based (warfarin, PAC/warfarin) group, NOAC-based (NOAC, PAC/NOAC) group. NOAC-based (NOAC, only group, PAC/NOAC) group. Analysis of variance, and chi-square test will be conducted for continuous variables, and categorical variables, respectively.
 - In order to distinguish between PAC bridging therapy and PAC treatment, we will apply a time restriction of 2 weeks to PAC bridging therapy.
- Temporal trend in anticoagulation therapy for VTE will be presented between 1 Mar 2013 and 30 Jun 2019. Proportions of the index OACs will be estimated according to calendar year and quarter.
- The number and percentage of patients who discontinue treatment completely, experience treatment interruption and treatment switch during their follow-up will be described by the index anticoagulant treatment received. Results will be limited to the first of each of these events for each patient. For patients experiencing a treatment switch, the new treatment will be described at the time of their first switcher per individual drug.
- The duration of the index treatment by the index anticoagulant treatment received will also be summarized in terms of days using descriptive statistics (mean [STD], median [IQR]).
- The Kaplan-Meier method will be applied to derive the empirical distribution of time to each of the treatment endpoints of interest (e.g., treatment discontinuation or switch); these analyses will be performed per index anticoagulant treatment received and no comparisons will be made. Log-rank test will be conducted at the 3-, and 6 months after treatment initiation to assess statistical significance between the survival curves. Persistent rate will also be calculated at the same time point.

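### The Phase I complete-discontinuation outcome checks only the index drug, and the overall anticoagulant duration is really index-treatment duration, so both labels claim more than the rules measure

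*SAP*

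**What the plan says.** SAP 8.4 sorts the end of the first treatment episode by three rules, and Protocol 9.3 words them in the same way.

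- **Switch.** Another anticoagulant must start no later than "within 30 days after the estimated end of supply of the index anticoagulant drug", and "exposure to the new anticoagulant treatment must last for at least 30 days to be considered as a treatment switch".
- **Interruption.** There is a gap of more than 30 days without treatment, "but subsequently restarts the index treatment after this period".
- **Discontinuation.** The outcome is introduced with the words "Treatment discontinuation (complete discontinuation; no reinitiation) will be defined as". The operative test is that the patient ended the first episode on the index treatment without switching and "subsequently have no further prescriptions for that respective anticoagulant treatment during all available follow-up time".

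On duration, the same section states: "Overall anticoagulant treatment duration will be defined as the time period from the index date to the earliest of treatment interruption, switch, or discontinuation". SAP section 10 uses a narrower name: "The duration of the index treatment by the index anticoagulant treatment received will also be summarized in terms of days". The shells of SAP Tables 5-8 return to the wider name, overall treatment duration.

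Tables 5-8 have rows for duration, 3- and 6-month persistence, switching, continuation, discontinuation, interruption and death. Tables 9-12 show the destination drug and time to switch, for switches only.

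**The concern.** The discontinuation label tells the reader that the patient stopped and did not restart. The rule establishes only that the index drug was not restarted. A patient can resume anticoagulation on another drug and still be counted as having stopped completely. Likewise, a reader of an overall anticoagulant duration will expect time on anticoagulation, but the clock stops when the patient changes drug.

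Both quantities are named in a Phase I primary objective (SAP section 6), and Phase I, unlike Phase II, is not conditional on a power assessment. Protocol 9.7 also plans Kaplan-Meier curves for these endpoints and log-rank tests among the three treatment groups. If the labels stand, index-drug stopping may be read and cited as the end of anticoagulation for Korean VTE patients.

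**Working it through.** The plan states no figure on this point, so there is nothing to reproduce. The check applies the SAP 8.4 rules to hypothetical patients.

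**Inputs from SAP 8.4:** a switch window of 30 days after index supply ends; at least 30 days on the new drug for a switch; interruption only if the index drug is restarted after the gap; otherwise discontinuation, tested on the index drug alone.

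**Assumptions:** the days are invented. The date of discontinuation or interruption is taken as the end of supply, because the documents do not define it. None of patients 1-5 or 7 returns to the index drug.

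**Formulas:** gap = start of other drug − end of index supply. Reported duration = date of switch, or end of supply if there is no switch. Days supplied = index days + days on the other drug.

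| Patient | Index supply ends | Other drug | Gap | Classified as | Reported duration | Days supplied, any anticoagulant |
|---|---|---|---|---|---|---|
| 1 | day 90 | from day 120, 180 days | 30 | switch | 120 | 90 + 180 = 270 |
| 2 | day 90 | from day 121, 180 days | 31 | discontinuation | 90 | 90 + 180 = 270 |
| 3 | day 90 | from day 135, 180 days | 45 | discontinuation | 90 | 90 + 180 = 270 |
| 4 | day 60 | from day 60, 180 days | 0 | switch | 60 | 60 + 180 = 240 |
| 5 | day 90 | from day 95, 20 days | 5 | discontinuation | 90 | 90 + 20 = 110 |
| 6 | day 90 | none; index drug restarted day 135 | – | interruption | 90 | – |
| 7 | day 90 | none | – | discontinuation | 90 | 90 |

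Three results follow.

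1. Patients 2, 3, 5 and 7 share the complete-discontinuation row, but only patient 7 had no further anticoagulant. One day's difference in the start date separates patient 1 from patient 2.
2. Patient 4 is correctly counted as a switch, yet the reported duration is 60 days against 240 days of unbroken anticoagulation.
3. No row of Tables 5-12 separates patients 2, 3 and 5 from patient 7, and none gives time on any anticoagulant.

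The 15- and 60-day grace periods do not resolve this. SAP section 10 lists them among the Phase II sensitivity analyses, and Table 20 reports them as hazard ratios for major bleeding. If a 60-day period also moved the switch window, which is not stated, patients 2 and 3 would become switches. Patient 5 would not, gaps over 60 days would still be discontinuations, and duration would still stop at the switch.

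**The case against.** The strongest defence is that these are index-treatment measures by design. The objective speaks of index anticoagulant treatment patterns, SAP section 10 calls the duration that of the index treatment, and the discontinuation rule says openly that it looks at the respective drug. Read this way, the rules form a coherent measure of index-drug persistence, and total time on anticoagulation is an additional quantity rather than one the plan mis-estimates. Phase I is descriptive, with no hypotheses set in advance. All of this stands as a defence of the rules. It does not defend labels that promise no reinitiation and an overall anticoagulant duration.

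A reader might infer that any change of drug is reported as the end of anticoagulation. The documents do not support that. A timely switch with at least 30 days on the new drug has its own count, timing and destination table; only duration and persistence treat it as an end. A late starter of another drug who later returns to the index drug meets the interruption wording. In Tables 5-6, where the group is NOAC-based, a late move between two NOACs might also be read as an interruption, because the documents do not say whether index treatment there means the drug or the group.

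A reader might also infer that warfarin will look worse, because SAP section 5 says "All NOACs became available as the first-line treatment of acute VTE in Korea after reimbursement expansion in May 2015". From March 2013 to April 2015 is 26 of the 76 index months (26/76 = 34%), and May 2015 to December 2019 gives up to 56 months in which to restart on a NOAC. But 34% is a share of calendar months, not of patients, and 56 months is an opportunity window, not a rate. Warfarin users who moved promptly and stayed on the new drug are coded as switches. NOAC users can also restart late on warfarin, another NOAC or a heparin. The direction is not established.

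**Conclusion.** The point holds as a mismatch between labels and rules that affects reported Phase I results. Some patients who started another anticoagulant will be counted under a label saying they did not reinitiate, and index-treatment time will be reported as overall anticoagulant time. This is more than a matter of wording, because no planned table lets the reader separate the two kinds of patient.

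Its size is unknown. The documents give no rate of late or brief use of a second anticoagulant after the index drug ends, and any assumed percentage of mislabelled discontinuations would simply return itself as the answer. The direction between drugs is likewise not computable. The example durations (60 against 240 days, 90 against 270) show what the rules can do to one patient; they do not estimate an average effect. Phase II sample size and power do not depend on this point.

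**What to change.** Amend SAP 8.4, Protocol 9.3 and the shells of Tables 5-8.

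- **Discontinuation.** Keep the present rule but call it index-treatment discontinuation. Split it into (a) no later prescription of any anticoagulant in follow-up, and (b) a later or brief prescription of a different anticoagulant (gap over 30 days, or exposure under 30 days). Reserve the label of complete discontinuation without reinitiation for (a). In the example, patient 7 goes to (a) and patients 2, 3 and 5 to (b).
- **Duration.** Rename the present measure index-treatment duration. Add duration on any anticoagulant, from the index date to the first gap of more than 30 days, carried through switches. Patient 4 would then show 240 days and patient 5 would show 95 + 20 = 115. Patients 2 and 3 would stay at 90 because their gap exceeds 30 days, so sub-row (b) is still needed to show them.

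Simply redefining discontinuation as no further prescription of any anticoagulant would be worse. A short heparin course years later would cancel a true stop, and a patient like number 5 would fit no category. The split keeps every patient classified.

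The cost is two sub-rows and one derived variable, from prescriptions already extracted. The proportion reported as complete discontinuation may be somewhat lower. Category (a) depends on length of follow-up, which should be noted under the tables: to 31 December 2019 it runs from about 6 months after a diagnosis at the end of June 2019 (up to 30 days less if treatment starts later) to about 82 months after one on 1 March 2013, and is shorter after in-hospital death.
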